7.2.2. Eligibility Criteria

HIV-negative adults and adolescents (at least 12 years of age) \geq 35kg initiating CAB LA for PrEP will be eligible for inclusion from the date of starting OLI or CAB LA injections.

7.3. Variables

7.3.1. Exposure definitions

All new users of CAB LA for PrEP per the approved SmPC for CAB oral and LA formulations will be included in the study. The study period will include OLI, followed by injectable long acting regimen use.

7.3.2. Outcome definitions

1) Incident HIV diagnoses – confirmation of HIV positive status:

- Frequency (number and proportion) of incident infections during CAB OLI and while adhering to CAB LA PrEP regimen will be assessed. Additionally, frequency of incident infections will be assessed among those initiating CAB OLI and those initiating DTI.
- HIV diagnosis through at least one of the following:
 - Positive HIV-1 antigen/antibody lab results as well as an HIV-RNA-based test; if a combined testing strategy including both tests is not available, testing should follow local guidelines while taking Apretude.
 - One detectable viral load

Incident HIV is any new HIV diagnosis that occurs after the initiation of CAB PrEP, having confirmed HIV negative status using HIV RNA test, at the time of PrEP initiation.

Prevalent HIV is defined as any undiagnosed HIV at the time of PrEP initiation and will be defined as positive HIV antigen/antibody test and/or positive viral load from sample collected at the time of initiation, following first prescription of CAB OLI and separately, following first CAB LA PrEP injection. Note the test result may be reported within 4-6 weeks after the sample was collected. Proportion and number of persons with prevalent and incident HIV will be reported for CAB OLI and CAB LA PrEP separately.

This study is designed to capture data documented in health records in real world clinical settings, provision of 4-6 weeks after starting PrEP for diagnosis included above accounts for time needed to obtain the diagnostic testing results, confirmation and uploading it to the health record. Assessment of 'prevalent infection' vs. 'incident infection' will take into consideration the date the diagnostic test sample was collected and sent to the lab for testing.

2) Proportion of individuals receiving CAB LA PrEP with HIV diagnosis

3) Time to incident HIV diagnosis

- a) Time to diagnosis will be defined as months from first CAB LA injection or OLI till the first confirmed positive HIV-1 antigen/antibody result, detectable viral load and HIV diagnosis.
- b) Time to HIV diagnosis will be shown separately for individuals infected during OLI and while adhering to CAB LA injection schedule.
- 4) ART regimen and VL testing among CAB PrEP users with prevalent and incident infections:

ART regimen and VL testing during the follow-up period for the following groups will be described:

- a) Individuals with incident infections
- b) Individuals with undiagnosed prevalent infections at the time of CAB PrEP initiation
- c) Durability of INSTI-based vs. non-INSTI based regimens (e.g., the numbers and proportions of those who achieve and maintain virologic suppression, the time to virologic suppression, the time to virologic breakthrough), as well as any INSTI resistance-associated substitutions that are detected upon ART failure

5) Adherence and Durability

- a) Adherence to CAB LA PrEP including OLI will be estimated from data collected via health record data
- b) Non-adherence to the dosing schedule will be assessed by:
 - Estimating the number of individuals that missed one or more consecutive injections without taking daily oral PrEP bridging while not on CAB LA injections and mean and median number of injections missed during a 6 and a 12-month period
 - Estimating the number of individuals who received the injections seven or more days later than their scheduled injection visit and median duration of delayed injections
 - Estimating the number of individuals who missed one or more consecutive injections without taking daily oral PrEP bridging or those who received the injections seven or more days later than their scheduled injection visit (Combined group a OR b) and describe characteristics for the individuals that are nonadherent
- c) Discontinuation will be defined as 2 injection cycles (~127 consecutive days) in which no injections were administered without oral PrEP bridging
- d) Describe the frequency and the regimen used for oral PrEP bridging to cover planned delayed or missed injections
- 6) Frequency of resistance to INSTIs and specific mutations among the following groups:
 - a) CAB LA PrEP started when the individual had undiagnosed HIV and subsequent emergence of resistance while on CAB monotherapy
 - b) CAB LA PrEP discontinued
 - without subsequent oral PrEP & potential risk of HIV acquistion and viral resistance during CAB LA PK tail
 - switched to oral PrEP and acquire HIV during the follow-up period and develop resistance during subsequent follow-up period while on treatment with ARVs
 - c) Incident HIV diagnosis while adhering to CAB LA for PrEP and development of resistance during treatment for HIV
- 7) Frequency of DILI and HSRs following CAB OLI and CAB LA injections assessed at 6, 12, 24, 36, and >36 months.

Hepatotoxicity related to administration of CAB for PrEP (i.e., DILI) as described below will be tabulated:

DILI case definition: Determination of suspected or potential DILI will be based on liver chemistry criteria (ALT, BILI and ALP) in addition to all relevant clinical information based on Aithal et al, 2011.⁵ An independent adjudication committee will review all potential and suspected cases of DILI that meet the liver chemistry criteria for DILI for drug attribution to CAB for PrEP. The adjudication committee will be provided with all relevant clinical information collected from data in the health records, to enable a comprehensive review and assessment of potential DILI attributed to CAB PrEP.

Liver chemistry criteria for DILI including any one of the following:

- a) More than or equal to fivefold elevation above the upper limit of normal (ULN) for ALT
- b) More than or equal to twofold elevation above the ULN for ALP (particularly with accompanying elevations in concentrations of 5'nucleotidase or γ-glutamyl transpeptidase in the absence of known bone pathology driving the rise in ALP level)
- c) More than or equal to threefold elevation in ALT concentration and simultaneous (within +/- 2 weeks) elevation of BILI concentration exceeding 2× ULN after starting CAB LA PrEP at 6, 12, 24, 36, and >36 months after initiation

If the person has had previous liver injury and hence abnormal LCT prior to starting CAB for PrEP, ULN is replaced by the mean baseline values obtained at baseline, (i.e., 5× baseline for ALT, 2x baseline for ALP and 2× baseline for BILI with associated 3× baseline elevation in ALT). Classification of the clinical severity of DILI involves use of the peak measured values for each of the biochemical parameters during the course of DILI.

Cases of suspected or potential DILI with attribution to CAB for PrEP will be tabulated according to the DILI severity grade as below:

Description of HSR: Signs and symptoms of HSR reported with INSTIs include, but are not limited to, severe rash, or rash accompanied by fever, general malaise, fatigue, muscle or joint aches, blisters, oral lesions, conjunctivitis, facial oedema, hepatitis, eosinophilia or angioedema. Clinical status, including liver transaminases, will be considered and frequency of HSRs will be assessed at 6, 12, 24, 36, and >36 months after study start.

HSRs have been reported in association with integrase inhibitors including cabotegravir. These reactions were characterised by rash, constitutional findings and sometimes organ dysfunction, including liver injury. Apretude and other suspected medicinal products should be discontinued immediately, should signs or symptoms of hypersensitivity develop (including, but not limited to, severe rash, or rash accompanied by fever, general malaise, fatigue, muscle or joint aches, blisters, oral lesions, conjunctivitis, facial oedema, hepatitis, eosinophilia or angioedema). Clinical status, including liver transaminases, will be considered, and frequency of HSRs will be assessed at 6, 12, 24, 36, and >36 months after study start.

All potential cases of HSR will be reviewed and confirmed by the independent adjudication committee. The committee will carefully assess all the signs and symptoms, and all relevant clinical information available in the health record, where considering the combination of events, time to onset of occurrence, organ systems involvement, evolution of outcome as well as characteristics and medical history may suggest an immediate or delayed type HSR to make the determination. The adjudication committee will be provided with all relevant clinical information collected from data in the health records, to enable a comprehensive review and assessment of potential HSRs attributed to CAB PrEP.

Regimen discontinuation will be reviewed, and cases of DILI or HSR will be confirmed by the adjudication committee. Discontinuation will be defined as 2 injection cycles (~127 consecutive days) in which no injections were administered without oral PrEP bridging.

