6. RESEARCH QUESTION AND OBJECTIVE(S)

The study will aim to assess usage patterns, adherence, effectiveness, safety, and resistance among individuals initiating CAB LA for PrEP.

The specific objectives are to assess:

- 1) CAB LA for PrEP usage pattern:
 - a. Describe the population initiating CAB LA for PrEP by:
 - i. Baseline demographics (age, sex, gender, ethnic origin, geographic region, BMI)
 - ii. Risk factors for HIV acquisition: STI diagnoses, substance use including injection drug use
 - iii. PrEP: History of previous PrEP use
 - iv. OLI or DTI: proportion of individuals who use OLI prior to initiating injections and proportion of individuals DTI

- b. Describe the individuals initiating CAB OLI or CAB LA PrEP with undiagnosed HIV acquisitions by baseline demographics and PrEP history
- c. Describe oral PrEP used to cover planned, delayed or missed CAB LA injections
- d. Assessing the frequency of testing for HIV and methods used for HIV-1 diagnosis, as well as assessing the timing of HIV testing relative to CAB LA for PrEP initiation injections and maintenance injections

Undiagnosed (prevalent) HIV acquisitions will be defined as positive laboratory HIV antigen/antibody test or positive viral load (RNA assay) following first prescription of CAB OLI and separately, following first CAB LA for PrEP injection. The date of the assay should be at the time of the first prescription or injection while the result may be reported within 4-6 weeks after first prescription or injection. Prevalent HIV will be shown for those who received CAB OLI and those who used DTI strategy.

- 2) Treatment adherence (Medication errors): Monitor for adherence by assessing the frequency of delayed and missed injections without oral PrEP bridging
 - a. Delayed and missed injections (non-adherence to the scheduled dosing)
 - i. Determine the number of individuals that miss one or more consecutive injections without daily oral PrEP bridging
 - ii. Assess the mean and median number of injections missed during the 6-month and 12-month period without oral PrEP bridging
 - iii. Determine the number of individuals who receive the injections seven or more days later than their scheduled injection visit and median duration of delay
 - iv. Describe characteristics of the individuals that are non-adherent
 - b. Discontinuation of CAB LA PrEP
 - i. Determine the proportion of individuals who discontinue CAB LA PrEP after 6, 12, 24, 36, and >36 months

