7.6. Data analysis

7.6.1. Essential analysis

Specific analytic methods are shown for each study objective. All CAB LA PrEP users will be followed for at least 3 years (36 months). All individuals with incident HIV acquisition will be followed through the end of the follow-up period. Participants discontinuing CAB LA PrEP will be monitored through the end of the follow-up period for HIV acquisition and, in the case of HIV acquisition, will be monitored for ART effectiveness and potential emergence of resistance.

In the event of a delay of ART initiation post HIV diagnosis, the study team will strive to follow the individual through the end of the follow-up period. Interim results will be generated at 12, 24, 36, 48 months since study initiation and final results will be generated at 60 months since study initiation.

Analysis for Objective 1 (Description of CAB for PrEP Usage pattern)

For individuals initiating CAB for PrEP, baseline demographics (age, sex, gender, ethnic origin (where available), BMI, geographic region), history of previous PrEP use and use of OLI prior to initiating injections will be described. Comorbidities, STIs, risk factors for HIV acquisition (e.g. HIV status of sexual partner, multiple sexual partners), will be reported as frequencies at baseline and at 6, 12, 24, 36, and >36 months of follow-up as available. Proportion of individuals using oral PrEP to cover planned, delayed or missed CAB LA injections will also be provided. Frequency of testing for HIV once initiated CAB for PrEP will be evaluated, and timing of HIV testing relative to injection dates will be assessed.

Prevalent HIV is defined as any undiagnosed HIV at the time of PrEP initiation and will be defined as positive HIV antigen/antibody test and/or positive viral load from sample collected at the time of initiation (first prescription of CAB oral lead and, separately, first CAB LA PrEP injection). Note the test result may be reported within 4-6 weeks after the sample was collected. Prevalent HIV will be reported at baseline while on CAB OLI and while on CAB LA. Also, prevalent HIV will be reported for those who received CAB OLI and separately for those with direct to injection (DTI) strategy. Incident HIV is any new HIV diagnosis that occurs after the initiation of CAB PrEP, having confirmed HIV negative status using HIV RNA test, at the time of PrEP initiation. Incident HIV reporting is described in objective 3.

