Frequency of undiagnosed prevalent HIV at CAB PrEP initiation will be assessed as described for objective 1. The primary effectiveness measure for objective 3 is proportion of individuals with incident HIV diagnosis during OLI and separately during CAB LA PrEP and will be calculated at 6, 12, 24, 36 months and over the entire length of follow-up. The proportion of incident infections among those who start with OLI and those who go to DTI will also be reported separately along with the timing of diagnosis of incident HIV acquisition for the overall group, and separately for the OLI and DTI groups.

Adherence patterns and characteristics of individuals with incident HIV diagnosis will be compared with those without incident HIV diagnosis, using t-test for continuous variables (Wilcoxon rank sum test for not normally distributed variables) or chi-square test for categorical variables. Participant characteristics significantly impacting acquisition of HIV based on univariate analysis will be selected for multivariable analysis. Risk for HIV acquisition and characteristics affecting risk for HIV acquisition will be assessed using negative binomial model with log-link function with binary outcome (HIV diagnosis vs not) if feasible.

Time to HIV diagnosis will be defined as time from first CAB LA PrEP injection to the first HIV diagnosis using laboratory antigen/antibody test, confirmed by viral RNA test. Time to HIV diagnosis will be assessed using Kaplan-Meier curve. Differences in time to diagnosis will be assessed by sex, gender, ethnicity (where available), geographic region, and risk factors (e.g. STI, previous PrEP usage) related, adherence to current PrEP to HIV acquisition. Additionally, time to diagnosis will be shown for people who acquired the infection while prescribed oral CAB lead in (if applicable). Time to diagnosis in this group will be defined as time from first CAB oral prescription to the first positive HIV-1 antigen/antibody lab result, confirmed by viral RNA test.

If feasible, Cox proportional hazards models will be constructed to compare time to HIV diagnosis by subgroup adjusting for additional variables (e.g., sex, ethnicity, (where available) geographic region).

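### A positive antigen/antibody test alone defines prevalent HIV at initiation even when the paired RNA is negative, and such a starter also meets the RNA-negative entry condition for incident HIV

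*Protocol*

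**What the plan says.** **Prevalent HIV.** Protocol section 7.3.2, item 1, describes prevalent HIV as undiagnosed HIV at PrEP initiation and then gives the working rule: "positive HIV antigen/antibody test and/or positive viral load from sample collected at the time of initiation". Section 7.6.1 (analysis for Objective 1) repeats the rule. Section 6 (Objective 1) has "positive laboratory HIV antigen/antibody test or positive viral load (RNA assay) following first prescription of CAB OLI". In all three places either test alone is sufficient.

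**Later diagnosis.** Section 7.3.2, item 1, accepts either of two routes. One is "Positive HIV-1 antigen/antibody lab results as well as an HIV-RNA-based test", with local guidelines applying where the combined strategy is not available. The other is a single detectable viral load. For time to diagnosis, section 7.6.1 (analysis for Objective 3) uses a "laboratory antigen/antibody test, confirmed by viral RNA test".

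**Entry condition for incident HIV.** Sections 7.3.2 and 7.6.1 require a new diagnosis after initiation in a person "having confirmed HIV negative status using HIV RNA test, at the time of PrEP initiation". A negative antigen/antibody test is not part of that condition.

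**Sorting and confirmation.** The choice between prevalent and incident "will take into consideration the date the diagnostic test sample was collected and sent to the lab for testing". Confirmation at baseline is mentioned only in explaining the 4-6 week window, which "accounts for time needed to obtain the diagnostic testing results, confirmation and uploading it to the health record".

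**The concern.** The rule for who already has HIV at the start is looser than the rule for who acquires it later, and the pair on which the two rules differ is not addressed. With a positive antigen/antibody test and a negative RNA at initiation, a person is a case of prevalent HIV as written and has also passed the RNA test that defines a negative start.

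The prevalent group will be very small, and three outputs depend on it: the description of people who start with undiagnosed HIV (section 6, Objective 1b), their ART and viral load results (7.3.2, outcome 4(b)), and resistance emerging on CAB monotherapy (section 6, Objective 5c; group a in the Objective 5 analysis). One or two false cases would change such a count materially.

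No later step in the protocol is set up to catch them. The adjudication committee is described for DILI, HSR and discontinuation, not for HIV status, and section 6 says no serum will be stored for later testing.

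**Working it through.** **Step 1: apply the written rules to each result pair.**

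| Antigen/antibody | RNA | Prevalent if found at initiation? | Meets RNA-negative entry for incident HIV? | A diagnosis if the same pair is found later? |
|---|---|---|---|---|
| Positive | Positive | Yes | No | Yes |
| Negative | Positive | Yes | No | Yes, by the viral-load route |
| Positive | Negative | **Yes** | **Yes** | **Not by the combined-test or viral-load route; possibly under local guidelines** |
| Positive | Not done | Yes | No | Only under local guidelines |
| Negative | Negative | No | Yes | No |

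The third row is the defect. The last column reads the combined-test route as requiring RNA support for the antigen/antibody result, which matches the RNA confirmation in the time-to-diagnosis analysis.

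**Step 2: does the third row count twice?** Incident HIV also needs a new diagnosis after initiation. Without one, the person is prevalent only. With one, both definitions are met. The sample-date provision places the baseline sample in time, but it does not say whether a discordant baseline is HIV or how such a person is classified once.

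**Step 3: check the protocol's own figures.** The protocol gives no figure for prevalent HIV. Its Table 1 concerns incident HIV. Exact Clopper-Pearson limits reproduce all 18 rows to within 0.0001 percentage points (for example N = 500 at 1.00%: 0.3255 to 2.3181). The present point does not affect that table.

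**Step 4: possible number of false cases.** The one input from the protocol is N = 500 (the target, section 7.4.1). Specificity is an assumption, with one test per starter.

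- Expected false positives = N × (1 − specificity)
- Probability of at least one = 1 − specificity^N

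| Assumed specificity | Expected false positives | Probability of at least one |
|---|---|---|
| 99.5% | 500 × 0.005 = 2.5 | 92% |
| 99.8% | 500 × 0.002 = 1.0 | 63% |
| 99.9% | 500 × 0.001 = 0.5 | 39% |
| 99.95% | 500 × 0.0005 = 0.25 | 22% |

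These are upper figures. They apply the error rate to every starter and make no deduction for positives resolved before entry.

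**Step 5: effect on the resistance proportion.** Suppose true prevalence is 0.2% (500 × 0.002 = 1 true case), that case develops resistance, and specificity is 99.8% (1 false case). If the false case stays in the denominator, the proportion is 1/2 = 50% instead of 1/1 = 100%. If only genotyped people are in the denominator, it stays 1/1. The Objective 5 analysis is based on genotypic data but does not say which denominator applies.

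**The case against.** The best defence is that the definition opens with undiagnosed HIV, stands under an item about confirming HIV-positive status, and explains the 4-6 week window partly by the time confirmation takes. The authors clearly mean true infection. The text also says positive, and a laboratory may use that word only after its own confirmation. This shows intent, but it does not set a criterion: the sentence goes on to state the working rule, and data will be coded to that rule.

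Several limits on the concern do stand.

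- A reader might infer that the discordant starter is counted as both prevalent and incident. The text does not support that, because incident HIV still needs a later diagnosis.
- A reader might infer that the resistance proportion will be diluted. That depends on keeping people without a genotype in the denominator, which the protocol leaves open.
- A reader might combine assumed specificity with an assumed true prevalence and conclude that most prevalent cases will be false. At a prevalence of 0.1% to 0.5% and the specificities above, the false share runs from 9% to 83%. That is a ratio of two assumed counts. It ignores the HIV-negative eligibility criterion (7.2.2), and it treats every discordant pair as false, although some may be true infections.
- The contrast with later diagnoses is weaker where the local-guidelines fallback applies.

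Finally, a sensitive baseline definition is a defensible choice for monitoring, and the study is descriptive. That argues for keeping unconfirmed positives visible, but not for merging them with confirmed infections.

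**Conclusion.** The point holds as an inconsistency in a stated case definition. As written, an antigen/antibody-positive, RNA-negative starter is prevalent HIV and also satisfies the RNA-negative start required for incident HIV. The overlap is one of eligibility and produces double classification only after a later diagnosis.

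False positives could inflate the prevalent count behind Objective 1b, outcome 4(b) and Objective 5c. They could lower the resistance proportion only if people without a genotype remain in its denominator.

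The size cannot be taken from the protocol. The illustrative range of 2.5 to 0.25 expected false cases in 500 starters rests on assumed specificity of 99.5% to 99.95%, one test each, and no allowance for positives settled before entry. It is small in absolute terms but matters because the group itself may be only a few people. Incident HIV, the primary effectiveness measure for Objective 3, and Table 1 are not shown to be wrong by this point. It should be corrected, and the correction is one of definition and reporting.

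**What to change.** Make the same change in sections 6, 7.3.2 and 7.6.1:

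1. Define *confirmed prevalent HIV* as an initiation sample that is RNA positive, or antigen/antibody positive with confirmation in the record by RNA, a supplementary assay or a second sample.
2. Put antigen/antibody-only positives without such confirmation, including those with a negative paired RNA, in a separate *unconfirmed* category.
3. Present Objective 1b, outcome 4(b) and Objective 5c for confirmed cases, with a sensitivity count that adds the unconfirmed ones.
4. State that prevalent and incident HIV are mutually exclusive, and how a person with an unconfirmed baseline positive and a later diagnosis is assigned to one of them.

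The cost is one definition, used in three places, and one extra category in the data capture system. It draws on results already in the record and asks for no extra tests, visits or stored samples. The drawback is that a few true infections without a recorded confirmatory test move to the unconfirmed category, where they are still reported.

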Apretude is given first as two initiation injections administered one month apart, and then every two months thereafter. Individuals can either start their treatment with Apretude, known as direct to injection (DTI), or take oral cabotegravir (Vocabria) for four weeks as an optional oral lead-in (OLI) to assess how well they tolerate the drug. Oral cabotegravir may also be used as oral PrEP in individuals who miss planned dosing with CAB LA injection.²

Efficacy assessment from pivotal studies (HPTN 083 and HPTN 084), designed to assess the safety and efficacy of CAB PrEP when compared to the active comparator daily oral TDF/FTC for HIV PrEP in the most key affected populations globally (i.e., MSM and TGW [enrolled in HPTN 083] and cisgender women [enrolled in HPTN 084]) demonstrated superiority.^{3,4}

In 083, CAB PrEP demonstrated superior efficacy among MSM and TGW when compared to daily oral TDF/FTC (HR 0.34; 95% CI 0.18 to 0.62, two-sided p=0.0005), with an approximate 66% reduction in the rate of incident infections. There were 39 HIV

incident infections in the TDF/FTC group (incidence rate 1.22/100 PY) and 13 incident infections occurred in the CAB group (incidence rate 0.40/100 PY).³

In 084, CAB PrEP demonstrated superior efficacy among cisgender women when compared to daily oral TDF/FTC (HR of 0.11 (95% CI 0.04 to 0.31), p<0.0001) demonstrating an 89% reduction in the rate of incident infections for CAB. There were 36 HIV incident infections in the TDF/FTC group (incidence rate 1.85/100 PY) and 4 HIV incident infections occurred in the CAB group (incidence rate 0.20/100 PY).⁴

CAB tablets are indicated for short term PrEP to reduce the risk of sexually acquired HIV-1 infection in at-risk individuals weighing at least 35 kg. The tablets may be used as:

- OLI for one month to assess tolerability of CAB prior to administration of the injection.
- Oral PrEP in individuals who miss planned dosing with CAB LA injection.

CAB LA injections are indicated for PrEP to reduce the risk of sexually acquired HIV-1 infection in at-risk individuals weighing at least 35 kg.

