Analysis for Objective 2 (Monitor for adherence by assessing the frequency of delayed and missed injections without oral PrEP bridging)

Adherence will be estimated using the dates of injections. Proportion and number of individuals with ≥ 1 delayed (≥ 7 days)and/or ≥ 1 missed injection without oral PrEP bridging over 6, 12, 24, 36, >36-month periods will be provided. Additionally, mean (median) number of delayed and missed injections will be provided for each period. Proportion and number of individuals with ≥ 7 days delay of CAB LA PrEP injection over 6, 12, 24, 36, >36-month periods will be provided. Additionally, mean (median) number of days delayed will be provided for each period.

Characteristics of persons with delayed or missed injections without oral PrEP bridging will be compared with those that are on time with the injections for 6, 12, 24, 36, and >36-month periods using t-test for continuous variables (Wilcoxon rank sum test for not normally distributed variables) or chi-square test for categorical variables.

Proportion and number of individuals who discontinue CAB LA PrEP over 6, 12, 24, 36, and >36-month-periods and overall will be provided. Additionally, distribution of individuals who discontinued by most common discontinuation reasons will be provided and will be used to understand whether individuals are missing injections or choosing to discontinue the regimen. Characteristics of persons who discontinue vs persons who stay on therapy will be compared for 6, 12, 24, 36, and >36-month periods using t-test for continuous variables (Wilcoxon rank sum test for not normally distributed variables) or chi-square test for categorical variables.

If feasible, risk of delayed or missed injections and separately risk of discontinuation will be assessed using negative binomial model with log-link function accounting for sex, age group, race/ethnicity, and other characteristics found significant in univariate analysis.

Analysis for Objective 3 (Effectiveness: Monitor for incidence of HIV diagnoses while on CAB for PrEP)

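### Oral PrEP bridging exempts a missed injection but not a late one, so the combined non-adherent group follows neither schedule adherence nor continuity of PrEP cover

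*Protocol*

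**What the plan says.** All references are to the protocol.

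- **Section 6, Objective 2 (stem):** "Monitor for adherence by assessing the frequency of delayed and missed injections without oral PrEP bridging".
- **Section 6, Objective 2(a)(i), missed limb:** "Determine the number of individuals that miss one or more consecutive injections without daily oral PrEP bridging".
- **Section 6, Objective 2(a)(iii), delayed limb:** "Determine the number of individuals who receive the injections seven or more days later than their scheduled injection visit and median duration of delay". There is no bridging condition.
- **Section 7.3.2 item 5(b):** the first two bullets repeat that split. The third joins them into one non-adherent group whose characteristics are to be described. Its missed limb requires absence of bridging; its delayed limb reads "or those who received the injections seven or more days later than their scheduled injection visit (Combined group a OR b").
- **Section 7.6.1, Objective 2:** "Characteristics of persons with delayed or missed injections without oral PrEP bridging will be compared with those that are on time with the injections". The same section also gives a separate count of delays of 7 days or more, with no bridging condition.

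The protocol expects bridging for delays as well as for missed doses. Objective 1(c) is to "Describe oral PrEP used to cover planned, delayed or missed CAB LA injections", and item 5(d) of section 7.3.2 plans the matching description. Section 5.1 says: "Oral cabotegravir may also be used as oral PrEP in individuals who miss planned dosing with CAB LA injection".

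**The concern.** Adherence is listed among the primary outcomes in the synopsis, and Objective 2 carries the label of medication errors. The combined group in item 5(b) is the one summary that merges the two kinds of departure from schedule, and it treats oral cover differently in each.

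Take two people who both take daily oral PrEP through a gap. One is injected 30 days late and enters the non-adherent group. The other misses the injection and does not. The description of non-adherent individuals then mixes people who had no cover with people who were covered, while leaving out other covered people with an injection gap. If section 7.6.1 uses a different group from section 7.3.2, one report would describe two populations under the same idea.

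**Working it through.** There is no stated figure to reproduce, because the point concerns a definition. The check is a truth table.

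**Step 1. Does the item 5(b) rule follow a single principle?** Under strict schedule adherence, any late or missed injection counts. Under continuity of cover, only an unbridged one counts.

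| Event | Bridged? | Item 5(b) combined rule | Strict schedule | Continuity of cover |
|---|---|---|---|---|
| On time | either | no | no | no |
| 7 or more days late | no | counted | counted | counted |
| 7 or more days late | yes | **counted** | counted | no |
| Missed | no | counted | counted | counted |
| Missed | yes | **no** | counted | no |

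The rule departs from strict schedule adherence in the last row and from continuity of cover in the third. Neither principle produces both cells. Discontinuation in item 5(c) is also conditional on absence of bridging, so within item 5 the delay limb is the exception.

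**Step 2. Does section 7.6.1 use the same group?** That depends on whether the bridging qualifier in the comparison sentence covers both nouns (natural reading) or only the missed injections (narrower reading).

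| Event | Item 5(b) | 7.6.1, natural reading | 7.6.1, narrower reading |
|---|---|---|---|
| Late, unbridged | non-adherent | delayed/missed group | delayed/missed group |
| Late, bridged | non-adherent | **neither group** | delayed/missed group |
| Missed, unbridged | non-adherent | delayed/missed group | delayed/missed group |
| Missed, bridged | not counted | neither group | **neither group** |
| On time | not counted | on-time group | on-time group |

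On the natural reading, bridged late users are non-adherent in section 7.3.2 and absent from the comparison in section 7.6.1. On the narrower reading the two sections agree about them, but bridged missed users are still in neither comparison group, and the asymmetry of step 1 is unchanged.

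**Step 3. Size, by assumption only.** The target of 500 participants is from section 7.4.1. Everything else here is assumed: 10% to 30% have at least one late injection, and 10% to 50% of those were bridged at every late injection and had no unbridged miss. The number who would leave the combined group if delays carried the same condition is N × P(late) × P(always bridged, given late):

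- Low end: 500 × 0.10 × 0.10 = 5 people, 5/500 = 1%.
- High end: 500 × 0.30 × 0.50 = 75 people, 75/500 = 15%.

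**The case against.** The strongest reply is that there is no contradiction. The Objective 2 stem is not a definition, and its qualifier can be attached to missed injections alone. Objective 2(a), item 5(b) and the counts in section 7.6.1 then agree. Item 5(b) is also framed as departure from the dosing schedule, and a late injection departs from it whatever oral PrEP was taken. This stands in part. A reader might infer a flat contradiction between the objective and its outcome definition; the wording supports one only on the natural reading. But the reply does not explain why a bridged miss, also a departure from schedule, is exempt.

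The second reply is that the two-person example relies on rules the protocol does not state. It does not say when a late injection becomes a missed one, or whether a planned gap moves the scheduled visit. A bridged user who skips an injection escapes only if the next one is not itself counted as late. Nor does the protocol define an adherent category, so such a user is merely not counted as non-adherent. All of this is correct. It limits how firmly the paradox can be asserted, but it also shows that the classification is under-specified.

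Third, the harm is contained. Missed and delayed counts are also reported separately, bridging is described under Objective 1(c) and item 5(d), and section 7.4.1 says no formal hypothesis is tested. That stands, and it lowers the severity. A delay count without a bridging condition is legitimate by itself; the defect lies in its use inside the combined group.

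**Conclusion.** The point holds as an inconsistency in an outcome definition that should be fixed. It does not undermine the study as a whole. On either reading, section 7.3.2 item 5(b) and Objective 2(a) count a bridged delay and exempt a bridged miss, and that follows no single concept of adherence. On the natural reading, the combined group also differs from the one compared in section 7.6.1.

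Two stronger conclusions are not supported. One is that the non-adherence proportion is inflated by a known amount: the documents give no frequency of late injections or of bridging, so the range of 5 to 75 people in 500 (1% to 15%) only illustrates the assumptions in step 3. The other is that the same error carries into the results for HIV diagnosed while adhering to the regimen: the protocol does not tie that phrase to item 5(b).

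**What to change.** Treat bridging in the same way for late and missed injections in sections 6, 7.3.2 and 7.6.1:

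1. Classify participants in each period at three levels: on time; late by 7 or more days or missed, with oral PrEP cover; late by 7 or more days or missed, without cover. State which level applies to a person with both covered and uncovered gaps.
2. Use the uncovered group as the combined non-adherence measure, in line with the Objective 2 stem, and use the same three levels in the 7.6.1 comparison so that no one drops out of it.
3. Keep the count and duration of all delays of 7 or more days, bridged or not, as a separate descriptive result.
4. State, for analysis purposes, when a late injection counts as missed.

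This concerns analysis classification only and changes no rule for managing participants. The cost is wording: injection dates (section 7.5) and bridging use (section 7.3.2 item 5(d)) are already planned data. The small downside is that the headline non-adherence proportion will be lower than under the current combined rule wherever bridged late users exist; the separate delay count keeps them visible.
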